#### 14.1.1 Primary Objective: Analysis of the primary endpoint confirmed BOR

Analysis (Analysis Population)	Derivation	Statistical Analysis Methods	Missing data handling
Primary endpoint: Confirmed Best Overall Response (BOR)			
Primary (FAS)	The confirmed BOR will be determined as the proportion of subjects with a confirmed CR or confirmed PR.	The frequency (number and percentage) of subjects with confirmed responses (defined as confirmed CR or confirmed PR) will be summarized by study cohort. For UC cohort will be summarized by stage and for stage 2 by treatment group. In stage 2 odds ratio will be displayed for treatment comparison. Additional for UC cohort Stage 1 and Stage 2 combination therapy group will be displayed together. Response rate with CI (Clopper-Pearson)	Participants with missing data are considered as non-responders

## 14.2 Secondary Endpoint: PFS time

Progression free survival time is defined as the time (in months) from treatment day 1 to the date of the first documentation of objective PD as per RECIST v1.1 or death due to any cause, whichever occurs first.

PFS data will be censored on the date of the last evaluable tumor assessment in the following cases:

- for participants who do not have an event (PD or death),
- for participants who started a new anti-cancer therapy prior to an event
- for participants with an event after two or more missing tumor assessments.

Participants who do not have a baseline tumor assessment or who do not have any post-baseline tumor assessments will be censored on the treatment day 1 unless death occurred on or before the time of the second planned tumor assessment in which case the death will be considered an event.

### 14.2.1 Secondary Objective: Analysis of the secondary endpoint PFS time

Analysis (Analysis Population)	Derivation	Statistical Analysis Methods	Missing data handling
Secondary endpoint: Progression Free Survival (PFS)			
Secondary (FAS)	time from treatment day 1 to the date of the first documentation of objective PD as per RECIST v1.1 or death due to any cause, whichever occurs first.	Kaplan-Meier estimates (product-limit estimates) will be presented by study cohort together with a summary of associated statistics (median time, 6-, 12-, 18-, 24-month rate estimates and estimates for every 6 months thereafter as applicable) including the corresponding two-sided 95% confidence intervals. The confidence intervals for the median will be calculated according to Brookmeyer and Crowley (1982). For UC cohort PFS results will be summarized by stage and for stage 2 by treatment group. In stage 2 hazard ratio will be displayed for treatment comparison. Additional for UC cohort Stage 1 and Stage 2 combination therapy group will be displayed together.	Model based

### Analyses of progression free survival time: additional information

The censoring and event date options to be considered for the PFS and DOR analyses are presented in the Table 2.

**Table 2 Outcome and Event Dates for PFS and DOR analyses**

Scenario	Date of event/censoring	Outcome
No adequate baseline assessment	Treatment Day 1	Censored a

Scenario	Date of event/censoring	Outcome
If the last tumor assessment is beyond 6 months from the first dose: Progression or death $\leq$ 12 weeks after last tumor assessment or $\leq$ 12 weeks after treatment day 1	Date of progression or death	Event
If the last tumor assessment is within 6 months from the first dose: Progression or death $\leq$ 8 weeks after last tumor assessment or $\leq$ 8 weeks after treatment day 1	Date of progression or death	Event
If the last tumor assessment is beyond 6 months from the first dose: Progression or death $>$ 12 weeks after the last tumor assessment	Date of last evaluable assessment	Censored
If the last tumor assessment is within 6 months from the first dose: Progression or death $>$ 8 weeks after the last tumor assessment	Date of last evaluable assessment	Censored
No progression	Date of last evaluable assessment	Censored
Treatment discontinuation due to 'Disease progression' without documented progression	Not applicable	Information is ignored. Outcome is derived based on documented progression only.
New anti-cancer therapy given	Date of last evaluable assessment before anti-cancer therapy is given	Censored
* However if the subject dies $\leq$ 12 weeks after treatment day 1 the death is an event with date on death date		

PFS (months) = [date of event or censoring – treatment day 1 +1]/30.4375

PFS will be summarized by dose level using the Kaplan-Meier method and displayed graphically when appropriate. Median event times and 2-sided 95% CIs for each median will be provided. Kaplan-Meier plots will also be provided.

The PFS time or censoring time and the reasons for censoring will also be presented in a participant listing.

Frequency (number and percentage) of participants with each event type (PD or death) and censoring reasons will be presented by study cohort. Reasons for censoring will be summarized according to the categories in Table 3 following the hierarchy shown.

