### Conversion factors

The following conversion factors will be used to convert days into months or years:  
1 month = 30.4375 days, 1 year = 365.25 days.

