**Table 3. PFS Censoring Reasons and Hierarchy**

Hierarchy	Condition	Censoring Reason
1	No adequate baseline assessment	No adequate baseline assessment
2	Start of new anti-cancer therapy before event.	Start of new anti-cancer therapy
3	Event more than 8 (or 12 if beyond 6 months from the first dose of study treatment) weeks after last adequate post-baseline tumor assessment/ date of first dose of study treatment (see here also Table 2)	Event after missing assessments a
4	No event and [withdrawal of consent date $\geq$ date of first dose of study treatment OR End of study (EOS) = Subject refused further FU]	Withdrawal of consent
5	No event and lost to follow-up in any disposition page	Lost to follow-up
6	No event and [EOS present OR disposition page for any tumor evaluation after screening says participant will not continue into any subsequent phase of the study] and no adequate post-baseline tumor assessment	No adequate post-baseline tumor assessment
7	No event and none of the conditions in the prior hierarchy are met	Ongoing without an event

a more than 8 (or 12) weeks after last adequate tumor assessment (see here also Table 2).

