#### **14.4 Secondary Endpoint: Duration of response**

Duration of response is defined, for participants with confirmed OR, as the time in months from first documentation of OR to the date of first documentation of PD as per RECIST v1.1 or death due to any cause. If a participant has not had an event (PD or death), DOR is censored. The censoring rules for DOR are the same as described below for PFS.

DOR will be summarized for the FAS of participants with a confirmed OR using the Kaplan-Meier method. The median event time and 2-sided 95% CI for the median will be provided. If the number of participants with a confirmed CR or PR is small, the data will only be listed.

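### IAP Table 2 censors PFS and DOR events after one scan interval, not the two missed scans of section 14.2, so progression at the scheduled week-36 scan is censored at week 24

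*SAP*

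**What the plan says.** All IAP references are to the expansion-cohort plan in the SAP document.

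- **Section 14.2 (text).** PFS is censored at the last evaluable assessment "for participants with an event after two or more missing tumor assessments". A participant with no baseline scan or no post-baseline scan is censored at the first dose date, with one exception: "unless death occurred on or before the time of the second planned tumor assessment in which case the death will be considered an event".
- **Table 2.** The outcome is censored at the last evaluable assessment in this case: "If the last tumor assessment is within 6 months from the first dose: Progression or death $>$ 8 weeks after the last tumor assessment". If the last scan is beyond 6 months, the limit is 12 weeks. The matching event rows use the same 8 and 12 weeks, counted from the last scan or from treatment day 1. A footnote says that if the subject dies within 12 "weeks after treatment day 1 the death is an event with date on death date".
- **Table 3.** The condition is "Event more than 8 (or 12 if beyond 6 months from the first dose of study treatment) weeks after last adequate post-baseline tumor assessment", labelled as an event after missing assessments, with a pointer back to Table 2.
- **DOR (section 14.4).** "The censoring rules for DOR are the same as described below for PFS".
- **Planned PFS outputs (section 14.2.1).** "median time, 6-, 12-, 18-, 24-month rate estimates and estimates for every 6 months thereafter as applicable".
- **Scan schedule (protocol Table 6, footnote g).** On treatment, scans are every 8 weeks for the first 6 months, at the end of Cycles 2, 4 and 6, and every 12 weeks after that. Each may be done up to 5 days early.

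**The concern.** Eight and 12 weeks are each one scan interval. Table 2 therefore censors an event after a single missed scan, where the text requires two, and a programmer cannot follow both. The case at the change from 8- to 12-week scanning is worse, because there Table 2 censors a participant who missed nothing.

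Censoring a participant because progression was found is informative. It removes the event and moves the observation back to the previous scan, so the bias runs one way, towards longer PFS and DOR. Protocol section 3.5.1.2 says DOR, PFS and OS are there to show whether responses bring lasting benefit, so the durability estimates are the ones affected. The IAP modification history records that sensitivity analyses of the efficacy criteria were removed in version 2.0, so no planned analysis would reveal the problem.

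**Working it through.** **1. Dates.** Cycles are 28 days, so on-treatment scans are due at weeks 8, 16, 24, 36, 48 and so on. The IAP conversion is "1 month = 30.4375 days, 1 year = 365.25 days", so 6 months = 6 × 30.4375 = 182.6 days. The week-24 scan is at 168 days, which is within 6 months, and the limit after it is 8 × 7 = 56 days.

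**2. Week 36.** 252 − 168 = 84 days, which exceeds 56. With either scan up to 5 days early the gap is 79 to 89 days, still above 56. Table 2 censors at (168 + 1)/30.4375 = 5.55 months. Section 14.2 finds no missed scan and counts an event at (252 + 1)/30.4375 = 8.31 months. The exception is an unscheduled scan after 6 months but before week 36, which brings in the 12-week limit.

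**3. The rules side by side, at nominal dates.**

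| Last scan (week) | Next scan, none missed | Table 2 | Section 14.2 | Scan after one missed | Table 2 | Section 14.2 |
|---|---|---|---|---|---|---|
| 8 | 16 | event | event | 24 | censored | event |
| 16 | 24 | event | event | 36 | censored | event |
| 24 | 36 | **censored** | event | 48 | censored | event |
| 36 | 48 | event | event | 60 | censored | event |

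The limits that section 14.2 implies are 16 weeks (24 − 8), 20 weeks (36 − 16) and 24 weeks (48 − 24, and the same afterwards). From day 1 the limit is 16 weeks.

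**4. Table 3.** If its 6-month condition is read by event date, the limit at week 36 is 84 days. Since 84 is not more than 84, the same progression is an event. Read through its pointer to Table 2, it is censored.

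**5. Scan window.** After week 8, if the earlier scan was 5 days early and the later one on time, the gap is 56 + 5 = 61 or 84 + 5 = 89 days, and an in-window progression is censored.

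**6. Deaths.** The second planned scan is week 16. Table 2 gives 12 weeks in the footnote and 8 weeks after day 1 in the row.

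**7. Size, hand check.** Assume exponential PFS with every event a progression and scans on schedule. The last scan before 12 months (365.25 days) is week 48 (336 days). Section 14.2 gives S(336). Table 2 removes the week-36 drop and gives S(168) × S(336)/S(252). For a 5-month median (152.2 days), S(d) = 2^(−d/152.2), so S(168) = 0.465, S(252) = 0.317 and S(336) = 0.217. The rates are 0.465 × 0.217/0.317 = 0.32 under Table 2 and 0.22 under section 14.2.

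**8. Size, with 10% of events as deaths.** Share of events censored = 0.9 × [S(168) − S(252)] + 0.1 × [S(224) − S(252)]. The Kaplan-Meier values come from simulation (400,000 per row).

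| True median (months) | Events lost | Lost of 16 | 12-month PFS: Table 2 vs 14.2 | KM median (weeks): Table 2 vs 14.2 |
|---|---|---|---|---|
| 3 | 12% | 2.0 | 0.14 vs 0.08 | 16 vs 16 |
| 5 | 14% | 2.2 | 0.30 vs 0.21 | 24 vs 24 |
| 8 | 12% | 2.0 | 0.48 vs 0.38 | 48 vs 36 |
| 12 | 10% | 1.6 | 0.61 vs 0.53 | 72 vs 60 |

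For the 5-month case the 18-month rate is 0.14 vs 0.10 and the 24-month rate 0.065 vs 0.046. The 6-month rate is essentially unchanged. Varying the death share from 0 to 20% gives a 12-month rate of 0.29–0.32 vs 0.21–0.22.

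**9. DOR, same model, response first seen at week 8.** The KM median is 40 vs 28 weeks for a true median of 6 months, and 52 vs 40 weeks for 9 months.

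**The case against.** The best case on the other side concerns practical weight.

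- **Early stopping.** The IAP history says the study was stopped early after the futility analysis, and section 6.1 opens Stage 2 only with 3 or more responders among 16. That suggests at most 2 responders in UC Stage 1 at that point, and section 14.4 only lists DOR when responders are few. The DOR medians above would then probably not be produced for that cohort. This stands, although a listing would still carry the wrong event status. Numbers in the other cohorts are not given.
- **Noise.** With 16 participants and a true rate of 0.21, the standard error is about √(0.21 × 0.79/16) = 0.10, similar to the 0.09 shift. This is fair, but the shift is systematic, whereas sampling error can go either way.
- **Intent.** Section 14.2 and the Table 3 label both speak of missed scans, and Table 3 can be read so that week 36 is an event. That supports correcting Table 2. It does not remove the literal wording, which ties the limit to the date of the last scan.
- **Schedule.** After end of treatment, Table 6 footnote g could be read as continuing 8-week scans past week 24, so the 84-day gap is certain only on treatment. If the 12 weeks were counted from month 6 instead, the next scan would be near week 38, and the gap would still exceed 8 weeks.
- **Scan timing.** How often step 5 occurs depends on actual scan dates, which the documents do not give. No figure for it should carry weight.
- **Footnote.** The Table 2 footnote mark does not match the mark in the table, so its scope is inferred. A conflict between 12 and 16 weeks remains on any reading.

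**Conclusion.** The point holds and should be fixed. The conflict between section 14.2 and Table 2, and the censoring of on-schedule week-36 progression, follow from the documents' own dates and need no model.

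The size does need one. With exponential PFS, on-schedule scans, 10% deaths and no other censoring, 10–14% of events are lost. The 12-month PFS rate rises by 0.06 to 0.10 for true medians of 3 to 12 months. The KM median moves only in the 8- and 12-month cases, by 12 weeks. Follow-up cut short by early stopping would reduce what is actually reported.

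The endpoints affected are secondary and the tests exploratory. Confirmed BOR, the futility rule and OS do not depend on these tables.

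**What to change.** Make Tables 2 and 3 carry out the section 14.2 rule: censor a progression or death only when two or more consecutive scheduled scans were missed. There are two ways to do it:

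- count missed visits against the schedule with its window; or
- set limits of 16 weeks after day 1 or the week-8 scan, 20 weeks after the week-16 scan, and 24 weeks after the week-24 scan or any later one, each plus 5 days.

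State in both tables that the limit is fixed by the date of the last scan. Set the death limits for participants without a baseline or post-baseline scan to the second planned assessment (week 16), and correct the footnote mark. Apply the same rule to DOR.

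The cost is IAP wording and programming. No new data are needed.

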**Table 3. PFS Censoring Reasons and Hierarchy**

Hierarchy	Condition	Censoring Reason
1	No adequate baseline assessment	No adequate baseline assessment
2	Start of new anti-cancer therapy before event.	Start of new anti-cancer therapy
3	Event more than 8 (or 12 if beyond 6 months from the first dose of study treatment) weeks after last adequate post-baseline tumor assessment/ date of first dose of study treatment (see here also Table 2)	Event after missing assessments a
4	No event and [withdrawal of consent date $\geq$ date of first dose of study treatment OR End of study (EOS) = Subject refused further FU]	Withdrawal of consent
5	No event and lost to follow-up in any disposition page	Lost to follow-up
6	No event and [EOS present OR disposition page for any tumor evaluation after screening says participant will not continue into any subsequent phase of the study] and no adequate post-baseline tumor assessment	No adequate post-baseline tumor assessment
7	No event and none of the conditions in the prior hierarchy are met	Ongoing without an event

a more than 8 (or 12) weeks after last adequate tumor assessment (see here also Table 2).

### 14.3 Secondary Endpoint: OS time

Overall survival (in months) is defined as the time from treatment day 1 to the date of death due to any cause. Participants known to be alive will be censored at date as specified in section 9 “last alive date” considerations.

OS (months) = [date of death or censoring – treatment day 1 +1]/30.4375

OS will be summarized and presented as PFS.

Frequency (number and percentage) of participants with event and censoring reasons will be presented by dose level. Censoring reasons are as follows:

- Ongoing in the study without an event

- Withdrawal of consent
- Lost to follow-up

The OS time or censoring time and the reasons for censoring will also be presented in a participant listing.

#### **14.4 Secondary Endpoint: Duration of response**

Duration of response is defined, for participants with confirmed OR, as the time in months from first documentation of OR to the date of first documentation of PD as per RECIST v1.1 or death due to any cause. If a participant has not had an event (PD or death), DOR is censored. The censoring rules for DOR are the same as described below for PFS.

DOR will be summarized for the FAS of participants with a confirmed OR using the Kaplan-Meier method. The median event time and 2-sided 95% CI for the median will be provided. If the number of participants with a confirmed CR or PR is small, the data will only be listed.

## 15 Safety Analyses

All safety analyses will be performed using the SAF by study cohort and overall, unless otherwise stated.

### 15.1 Adverse Events

#### Definitions

**Treatment-emergent adverse events:** those events with onset dates occurring during the on-treatment period for the first time, or if the worsening of an event is during the on-treatment period as defined in Section 9.

**Treatment Related Adverse Events (TRAE):** adverse events with relationship to avelumab and/or NHS-IL12 (as recorded on the AE eCRF page, Relationship with study treatment = Related) reported by the investigator.

**Serious Adverse Events (SAEs):** serious adverse events (as recorded on the AE eCRF page, Serious Adverse Event = Yes).

**Adverse Events Leading to Any Treatment Discontinuation:** adverse events leading to permanent discontinuation of study treatment (as recorded on the AE eCRF page, Action taken with any study drug = Drug withdrawn).

**Adverse Events Leading to Death:** adverse event leading to death (as recorded on the AE eCRF page, Outcome = Fatal, as well as AEs of Grade 5).

**Immune-Related Adverse Events (irAEs):** Immune-Related adverse events (please refer to the section 18.4)

**Infusion-Related Reactions (IRRs):** IRRs (please refer to the section 18.4).

CCI

CCI

### Missing data handling

Missing data imputation is described in Section 9.

#### 15.1.1 All Adverse Events

Unless otherwise stated, adverse events will be displayed in terms of frequency tables: by study cohort, primary SOC and PT in decreasing frequency.

Adverse events will be summarized by worst severity (according to NCI-CTCAE version 4.03) per participant, using preferred term as event category and primary system organ class (SOC).

If an adverse event is reported for a given participant more than once during study intervention, the worst severity and the worst relationship to study intervention will be tabulated.

The following tables will be created:

- The overall summary of AEs table will include the frequency (number and percentage) of participants with each of the following by study cohort and overall:
  - TEAEs
  - TEAEs, Grade  $\geq 3$
  - CCI
  - CCI
  - Serious TEAEs
  - CCI
  - TEAEs leading to death
  - CCI
  - All irAEs
  - CCI
  - All IRRs
  - CCI
  - Any Infusion-Related Reaction Leading to Death

- Any Infusion-Related Reaction Grade  $\geq 3$
- Any Serious Infusion-Related Reaction
- Any Immune-Related Reaction
- Any Immune-Related Reaction Leading to Death
- Any Immune-Related Reaction Grade  $\geq 3$
- Any Serious Immune-Related Reaction
- CCI [REDACTED]
- Any TEAEs by SOC and PT
- Any TEAEs by SOC and PT and worst grade
- CCI [REDACTED]
- CCI [REDACTED]
- TEAEs leading to death by SOC and PT
- CCI [REDACTED]
- TEAEs Excluding SAEs, with Frequency  $\geq 5\%$  in any dose level by SOC and PT
- Serious TEAEs, with Frequency  $\geq 5\%$  in any dose level by SOC and PT

#### Evaluation of COVID-19 effect on AEs

The direct effect of COVID-19 for AEs will be assessed via a listing of COVID-19 related AEs including the relevant information. The listing will be generated using the “COVID-19 related terms MedDRA 23.0 update Spreadsheet” (<https://www.meddra.org/covid-19-related-terms-meddra-230-update-spreadsheet>) or a later version as available from Maintenance and Support Services Organization (MSSO), considering all “search terms for COVID-19-related” = “Y”.

### **15.1.2 Adverse Events Leading to Study Discontinuation**

The number and percentage of participants with each of the following events will be presented for TEAEs leading to permanent discontinuation in an overall summary table by study cohort and overall:

- TEAEs leading to study drug discontinuation (both drugs, avelumab, NHS-IL12)
- Avelumab related TEAEs leading to study drug discontinuation (any drug, avelumab, NHS-IL12)
- NHS-IL12 related TEAEs leading to study drug discontinuation (any drug, avelumab, NHS-IL12)
- irAEs leading to permanent avelumab discontinuation
- IRRs leading to permanent avelumab discontinuation
- Cytokine release syndrome TEAEs leading to permanent discontinuation of NHS-IL12
- Cytokine release syndrome TEAEs leading to permanent discontinuation of avelumab

The following summaries by SOC and PT will be produced:

- TEAEs Leading to avelumab Permanent Discontinuation by SOC and PT
- TEAEs Leading to NHS-IL12 Permanent Discontinuation by SOC and PT
- TEAEs Leading to avelumab and NHS-IL12 Permanent Discontinuation by SOC and PT
- Avelumab related AEs Leading to avelumab Permanent Discontinuation by SOC and PT
- NHS-IL12 related AEs Leading to NHS-IL12 Permanent Discontinuation by SOC and PT

The listing of all AEs leading to treatment discontinuation will also be provided with the relevant information.

### **15.2 Deaths, Other Serious Adverse Events, and Other Significant Adverse Events**

#### **15.2.1 Deaths**

The frequency (number and percentage) of participants who died will be tabulated based on information from the “Death” eCRF page by study cohort and overall.

- All deaths will be tabulated and listed for SAF analysis set. The deaths table will include the following information:
  - Number and percentage of participants who died

- Primary reason for death
  - Disease progression
  - Adverse event related to study treatment
  - Adverse event not related to study treatment
  - Other
  - Unknown
- Number and percentage of participants who died within 30 days of the last study treatment administration
  - Primary reason for death
    - Disease progression
    - Adverse event related to study treatment
    - Adverse event not related to study treatment
    - Other
    - Unknown
- Number and percentage of participants who died within 60 days of the first study treatment administration
  - Primary reason for death
    - Disease progression
    - Adverse event related to study treatment
    - Adverse event not related to study treatment
    - Other
    - Unknown

In addition, date and cause of death will be provided in individual participant data listing together with selected dosing information (study treatment received, date of first / last administration, study cohort) and will include the following information:

- AEs with fatal outcome (list preferred terms of AEs with outcome=Fatal, as well as AEs of Grade 5),
- Flag for death within 30 days of last dose of study treatment.
- Flag for death within 60 days of first dose of study treatment.

